7.1.3 Myalgias and Myopathy

Persons who present with significant myalgias (Grade ≥ 3 , ie, muscle pain causing inability to perform usual social and functional activities) should be evaluated with a clinical assessment that includes an evaluation of CK, serum creatinine, potassium, and urinalysis. Myopathy is defined as muscle aches, soreness, tenderness, or weakness with creatinine kinase (CK) $>10 \times$ ULN not related to exercise or other causes, including trauma. If the symptoms are associated with Grade ≥ 3 elevation in CK ($10 \times$ ULN) (see table below) that is not related to exercise or other cause, study medications should be permanently discontinued. Subjects will be followed on study, off treatment through the study termination visit with subject evaluations as per section 6.2.4.

NOTE: Mitochondrial toxicity related to nucleoside therapy and not related to study medication is a possibility, and evaluations for lactic acidosis should be considered by the subject's primary care provider.

Serum CK Toxicity Grading*

Toxicity Grade	Value
Grade 1	$3 - <6 \times$ ULN
Grade 2	$6 - <10 \times$ ULN
Grade 3	$10 - <20 \times$ ULN
Grade 4	$\geq 20 \times$ ULN

* Not related to exercise or other cause

7.1.4 Rhabdomyolysis

Rhabdomyolysis is defined as the presence of myopathy as per section 7.1.3 plus one or more of the following:

- Hematuria on urine dipstick in the absence of microscopic hematuria (myoglobinuria)
- Grade ≥ 2 hyperkalemia
- Grade ≥ 2 creatinine elevation

If rhabdomyolysis occurs, study medications should be permanently discontinued. The team should be consulted. Subjects will be followed on study, off treatment through the study termination visit with subject evaluations as per section 6.2.4. In addition, CK will be added to the laboratory evaluations performed until it has declined to $\leq 1 \times$ ULN.

7.2 Requirement for Precautionary or Prohibited Medications (see PSWP)

Subjects who need to initiate therapy with erythromycin, colchicine, cyclosporine, or rifampin should be asked to hold study drug. If use of one of these precautionary medications is anticipated to be short-term, the site investigator may consider restarting study drug after use of prohibited medication is discontinued.

Subjects who begin a statin medication provided through clinical care should discontinue study drug. Taking two statins can increase the risk of toxicity.

Subjects who temporarily or permanently discontinue study treatment will be followed on study, off treatment through the study termination visit with subject evaluations as per section 6.2.4.

7.3 Pregnancy

If the pregnancy test is positive at entry, then the subject should not start study treatment. No further evaluations are necessary, provided that the subject did not initiate study drug.

Subjects who become pregnant after study entry must discontinue study treatment immediately. These subjects should be seen for a premature treatment discontinuation evaluation within 7 days. The core team must be notified of any pregnancies that occur in subjects on study.

All pregnancies should be followed until the final outcome can be determined. Pregnancies that occur on study should be reported prospectively to The Antiretroviral Pregnancy Registry. More information is available at www.apregistry.com. [contact]; [contact] (Non-US sites: [contact] or [contact]; [contact].)

8.0 CRITERIA FOR DISCONTINUATION

8.1 Permanent Study Treatment Discontinuation

- Drug-related toxicity requiring permanent study treatment discontinuation (see section 7.0)
- Requirement for prohibited concomitant medications (see section 5.4)
- Pregnancy
- Breast-feeding
- Completion of treatment as defined in the protocol
- Request by subject to terminate treatment
- Clinical reasons believed life threatening by the physician, even if not addressed in the toxicity section of the protocol
- Failure by the subject to attend 2 consecutive clinic visits

8.2 Premature Study Discontinuation

- Request by the subject to withdraw
- Request of the primary care provider or investigator if s/he thinks the study is no longer in the best interest of the subject
- Subject judged by the investigator to be at significant risk of failing to comply with the provisions of the protocol as to cause harm to self or seriously interfere with the validity of the study results
- At the discretion of the IRB, FDA, IND sponsor, or pharmaceutical supporters

9.0 STATISTICAL CONSIDERATIONS

9.1 General Design Issues

HILLCLIMBER is a randomized, controlled, open-label phase II trial. 40 subjects not already on high dose statin therapy who have CHD and/or calculated 10-year ASCVD risk >15% will be included and started on moderate dose statin therapy (pravastatin 40mg daily) for an initial two-week run-in period. Subjects not demonstrating significant toxicity at week 2 will then be randomized to high intensity statin therapy (rosuvastatin 20mg) versus continuing moderate intensity statin therapy (pravastatin 40mg daily). At week 6, subjects in the rosuvastatin arm who do not demonstrate significant toxicity and whose LDL-c is >60mg/dl and decreased by less than 25% compared with week 2 will then have doses increased to rosuvastatin 40mg (high dose group). Efficacy and safety will be evaluated at Week 14.

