HILLCLIMBER is a randomized, controlled, open-label phase II trial of moderate dose statin therapy versus high-dose statin therapy in HIV-infected persons taking antiretroviral therapy (ART) who have coronary heart disease (CHD) or are at high risk for atherosclerotic cardiovascular disease. All subjects will have an initial two-week run-in period with pravastatin 40mg daily. Subjects not demonstrating significant toxicity at week 2 will then be randomized to rosuvastatin 20mg versus continuing pravastatin 40mg daily. At week 6; those in the rosuvastatin arm who do not demonstrate significant clinical or laboratory safety/toxicity issues will then have doses increased to rosuvastatin 40mg (high intensity dose group). The group randomized to pravastatin 40mg daily at week 2 will not have their dose increased at the end of week 6 (moderate intensity group).

- The primary endpoint is percent change in low-density lipoprotein cholesterol (LDL-c) from Week 2 to 14 of high versus moderate intensity lipid-lowering statin therapy

DURATION

Total duration of the study is 14 weeks: 2 weeks for the initial run-in, 12 weeks on therapy as per randomization (weeks 6-14 with possible dose increase).

SAMPLE SIZE

40 subjects

POPULATION

HIV-infected subjects not already on high dose statin therapy who have coronary heart disease (CHD) or are at high risk for atherosclerotic cardiovascular disease (ASCVD, which includes myocardial infarction and stroke) as evidenced by 10-year ASCVD risk of 15.0% or greater.

REGIMEN

The following treatment regimens will be used:

Stage One (Run-in): Pravastatin 40mg daily (Weeks 0-2),

Stage Two (Randomization in 1:1 ratio):

- Moderate intensity group: Pravastatin 40mg daily (Weeks 2-14)

OR

- High intensity group: Rosuvastatin 20mg daily (Weeks 2-6), titrated to Rosuvastatin 40mg daily (Weeks 6-14).

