3.0 STUDY DESIGN

This is a single center, randomized, controlled, open-label phase II trial. Up to 40 subjects not already on high dose statin therapy who have documented CHD and/or calculated 10-year ASCVD risk >15% will be included and started on moderate dose statin therapy (pravastatin 40mg daily) for an initial two-week run-in period. Subjects not demonstrating significant toxicity at week 2 will then be randomized to rosuvastatin 20mg versus continuing pravastatin 40mg daily. Subjects will return at week 6; those in the rosuvastatin arm who do not demonstrate significant safety or toxicity concerns will then have doses increased to rosuvastatin 40mg (high dose group). The group randomized to pravastatin 40mg daily at week 2 will not have their dose increased at the end of week 6.

The following treatment regimens will be used:

Stage One (Run-in): Pravastatin 40mg daily (Weeks 0-2),

Stage Two (Randomization in 1:1 ratio):

- Moderate intensity group: Pravastatin 40mg daily (Weeks 2-14)
OR
- High intensity group: Rosuvastatin 20mg daily (Weeks 2-6), potentially titrated to Rosuvastatin 40mg daily (Weeks 6-14).

Total duration of the study is 14 weeks: 2 weeks for the initial run-in, 6 weeks following randomization, and 6 weeks following dose increase.

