5.0 STUDY TREATMENT

5.1 Regimens, Administration, and Duration

After a 2-week pravastatin 40mg daily run-in period, subjects will be randomly assigned to rosuvastatin 20mg daily or pravastatin 40mg daily at week 2 in a 1:1 ratio. At week 6, subjects on the Rosuvastatin arm may have their dose escalated to 40mg daily.

Run-in: Pravastatin 40mg daily for 2 weeks (Weeks 0-2)

Randomization (1:1 ratio) at Week 2:

- Moderate intensity strategy: Pravastatin 40mg once daily for 12 weeks (Weeks 2-14)
OR
- High-intensity strategy: Rosuvastatin 20mg once daily for 4 weeks (Weeks 2 to 6)
 - Continue Rosuvastatin 20 mg once daily (Weeks 6 to 14) if:
 - AST or ALT between 1.5x and 3x ULN
OR
 - CK between 3x and 10x ULN
OR
 - Grade 1 or 2 toxicity attributable to rosuvastatin is present
 - Escalation of Rosuvastatin to 40 mg daily (Weeks 6 to 14) if:
 - AST, ALT, and CK \leq 1.5x ULN at week 6
AND
 - CK \leq 3x ULN at week 6
AND
 - No grade 1 or greater toxicity attributable to rosuvastatin is present

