5.1.1 Regimen

Subjects should begin study treatment within 72 hours after entry and continue on study treatment for 14 weeks.

Study drugs will be supplied in bottles for this open-label study. The pharmacist will dispense 2 weeks (15 tablets) of pravastatin 40 mg at week 0 to all participants. At week 2, subjects will be randomized to receive either 12 weeks (3 bottles, 90 tablets) of rosuvastatin 20 mg tablets or 12 weeks (85 tablets) of pravastatin 40 mg tablets.

Based on LFTs, CK, and safety/toxicity assessments at Week 6, participants in the rosuvastatin arm will be notified within 5 days whether or not they are to escalate to two 20mg tablets daily or continue taking one tablet daily. If the dose is escalated, participants will need to return to the pharmacy within the next 4 weeks to receive an additional supply of 30 tablets (1 bottle) of rosuvastatin 20mg.

At the Week 14 visit, subjects should return any remaining study-provided study products.

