7.0 CLINICAL MANAGEMENT ISSUES

7.1 Toxicity Management

Criteria for subject management, dose interruptions, modifications, and discontinuation of study treatment will be mandated only for toxicities attributable to study-provided drugs (pravastatin and rosuvastatin).

The grading system for drug toxicities is the DAIDS Table for Grading the Severity of Adult and Pediatric Adverse Events, Version 2.0, November 2014, located at <http://rsc.tech-res.com/safetyandpharmacovigilance/gradingtables.aspx>.

The lone difference between the grading system for drug toxicities used in this trial and the DAIDS Table is that our protocol has a lower threshold for grading transaminase (AST and ALT) elevations; based on the current ACC/AHA and National Lipid Association Guidelines, we consider elevation of AST or ALT ≥ 3 x ULN as grounds for holding the study drug (and a grade 3 adverse event in this protocol), and CK ≥ 10 x ULN as a grade 3 adverse event and grounds for holding the study drug.

NOTE: The HILLCLIMBER protocol chair must be notified by e-mail regarding toxicities that result in regimen interruption or discontinuation. Email: [contact]. General guidelines presented in sections 7.1.1 to 7.1.3 apply to toxicities that are not specifically discussed further below.

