9.2 Endpoints

9.2.1 Primary Endpoints:

Efficacy: The primary efficacy endpoint is mean percent change in fasting LDL-c (mg/dl) from week 2 (end of run-in period) to week 14

- The mean percent change in fasting LDL-c from week 2 to week 14 will be compared for the high dose group (rosuvastatin 20mg daily uptitrated to 40mg daily) and the moderate dose group (pravastatin 40mg daily).

Safety:

- All treatment-emergent adverse events, including but not limited to:
 - Incidence of adverse event-related study drug discontinuation (following initial 2 week wash-in) or hospitalizations
 - Grade 3 or greater adverse events;
 - Study drug-related symptoms
 - CK elevation > 3x upper limit of normal;
 - AST or ALT elevation >3x upper limit of normal;

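### Section 9.1 adds two LDL-c conditions to the week-6 increase to rosuvastatin 40 mg that the synopsis and Sections 3.0, 5.1 and 5.1.1 do not contain

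*Combined protocol and SAP*

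**What the plan says.** Five places in the combined protocol and SAP describe the week-6 decision in the rosuvastatin arm.

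- **Synopsis:** "those in the rosuvastatin arm who do not demonstrate significant clinical or laboratory safety/toxicity issues will then have doses increased to rosuvastatin 40mg".
- **Section 3.0:** "those in the rosuvastatin arm who do not demonstrate significant safety or toxicity concerns will then have doses increased to rosuvastatin 40mg".
- **Section 5.1:** lists AST, ALT and CK limits, plus the condition "No grade 1 or greater toxicity attributable to rosuvastatin is present". There is no LDL-c criterion.
- **Section 5.1.1:** "Based on LFTs, CK, and safety/toxicity assessments at Week 6, participants in the rosuvastatin arm will be notified within 5 days" whether to go to two tablets or stay on one. LDL-c is not among the inputs.
- **Section 9.1:** increases the dose only for patients without significant toxicity "whose LDL-c is >60mg/dl and decreased by less than 25% compared with week 2 will then have doses increased to rosuvastatin 40mg".

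Section 9.2.1 labels the experimental arm the "high dose group (rosuvastatin 20mg daily uptitrated to 40mg daily", again with no LDL-c condition. Section 9.4 gives expected mean LDL-c of 75 mg/dl on pravastatin and 50 mg/dl on rosuvastatin, with SD 20.

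**The concern.** A patient who tolerates 20 mg and whose LDL-c is 60 mg/dl or lower, or has fallen by 25% or more, goes to 40 mg under 5.1 and by implication stays on 20 mg under 9.1. These are two different strategies. One titrates everyone who tolerates the drug; the other titrates only poor responders. Whichever rule staff follow, they depart from the other.

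Section 2.1 says no trial has tested rosuvastatin 20–40 mg in people on ART, and Section 2.0 calls this a pilot for later safety and efficacy studies. The amount of experience at 40 mg is therefore one of the main things the trial can deliver, and it depends on which rule applies. So does whether the 9.2.1 label describes the arm.

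**Working it through.** **1. The plan's own figure.** Section 9.4: difference 25 mg/dl, SD 20, two-sided alpha 0.05, power 0.80. n per arm = 2 × (1.960 + 0.842)² × 20² / 25² = 10.05, rounded up to 11. This matches the plan and does not depend on the titration rule.

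**2. The average patient.** Taking 75 mg/dl as the week-2 mean and 50 mg/dl as the week-6 mean (assumption), the fall is (75 − 50)/75 = 33%. The predicted reductions in 9.4 (pravastatin 30%, rosuvastatin 20 mg 55–60%) give 1 − 0.45/0.70 = 36% to 1 − 0.40/0.70 = 43%, if the pravastatin effect is complete at week 2 (assumption). All exceed 25%, and 50 is below 60, so the average patient fails both conditions in 9.1.

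**3. Share meeting both conditions.** Let W2 and W6 be bivariate normal, SD 20 each, with correlation r. The documents give no r, so 0 to 0.9 is tried. Needed: P(W6 > 60 and W6 > 0.75 × W2).

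| Means, week 2 / week 6 | r = 0 | r = 0.5 | r = 0.9 | Rules differ for |
|---|---|---|---|---|
| 75 / 50 (9.4 planning values) | 0.253 | 0.218 | 0.172 | 75–83% |
| 95 / 62 (9.4 landmark-trial means) | 0.322 | 0.264 | 0.148 | 68–85% |
| 75 / 55 (assumption) | 0.335 | 0.307 | 0.299 | 66–70% |
| 75 / 60 (assumption) | 0.425 | 0.410 | 0.441 | 56–59% |
| 75 / 65 (assumption) | 0.519 | 0.518 | 0.573 | 43–49% |

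The last column is one minus the share meeting both, among patients who pass the safety criteria, with tolerability taken as independent of LDL-c. At the planning values, the 60 mg/dl condition alone excludes P(Z ≤ (60 − 50)/20) = 69%.

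**4. Exposure at 40 mg.** Assume 15–20 patients pass the safety criteria. Section 5.1.1 dispenses 90 tablets of 20 mg, and 30 more on escalation.

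- Escalation at day 28: 120 − 28 = 92 tablets, 46 days at two a day, 6.6 weeks.
- Escalation 5 days later: 120 − 33 = 87 tablets, 43.5 days, 6.2 weeks.
- Under 5.1: 15 × 6.2 = 93 to 20 × 6.6 = 131 patient-weeks (on the nominal 8 weeks, 120 to 160).
- Under 9.1 at planning values: 0.172 × 93 = 16 to 0.253 × 131 = 33 patient-weeks (nominal, 21 to 40).

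The ratio is 17–25%, about a fifth, whichever duration is used.

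**5. Effect on the primary contrast.** Moving from 20 to 40 mg, relative to week 2 and comparing like ends of the 9.4 ranges: (60 − 55)/70 = 7.1 points at the lower ends and (63 − 60)/70 = 4.3 points at the upper ends. This compares everyone escalated with no one escalated, so the difference between the two rules is smaller still. Pairing opposite ends gives 0 to (63 − 55)/70 = 11.4 points, an extreme range. The expected contrast is 33 points from the LDL-c levels and up to 1 − 0.37/0.70 = 47 points from the predicted reductions.

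**The case against.** The strongest defence is that 5.1 and 5.1.1 are the operative text. They hold the explicit criteria, the inputs and the notification step. The synopsis and 3.0 agree with them, and the trial has one center. Section 9.1 is one sentence in a statistical recap and never states outright that the remaining patients stay on 20 mg. Parts of the synopsis, 3.0 and 5.1 also describe the increase as possible rather than certain. The plan treats rosuvastatin 20–40 mg as one high-intensity range, so a patient left on 20 mg is still on the assigned strategy.

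Much of this stands, and it lowers the severity. It does not remove the conflict. The permissive phrases fit patients who fail the safety criteria, while the directive sentences and the 5.1 list contain no LDL-c test. Section 9.1 gives numerical thresholds, and the week-6 fasting lipid panel in 6.1 makes them usable.

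A reader might infer more than the documents support:

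- **That most patients certainly receive conflicting instructions.** The 75 and 50 mg/dl are expected group levels, with 50 for the whole 20–40 mg arm; they are not stated as week-2 and week-6 values. The landmark means compare parallel groups, one of them on atorvastatin 80 mg.
- **That the primary comparison or sample size is undermined.** Section 9.6.1 compares randomized strategies by intention to treat, and 11 per arm reproduces under either rule.
- **That the toxicity bar also differs in substance.** The undefined reference to significant toxicity in the synopsis, 3.0 and 9.1 can be read as shorthand for the 5.1 criteria.

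**Conclusion.** The inconsistency is real and unreconciled: 9.1 conditions escalation on LDL-c, and four other places do not. At the planning values the rules differ for about 75–83% of tolerating patients. This rests on normality, SD 20 at both visits, an unknown correlation of 0 to 0.9, and reading the 9.4 means as week-2 and week-6 levels. The majority holds up to a week-6 mean of about 60 mg/dl and is lost at 65.

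The consequence is the number of patients reaching 40 mg and the safety exposure there. The effect on the primary contrast is small. It should be fixed, but it does not threaten the trial's main comparison.

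The CK limits are a separate problem and do not add to the weight of this point. Section 5.1 continues 20 mg for "CK between 3x and 10x ULN"; 9.5 discontinues study drug at CK of 3 times ULN or more at weeks 2, 6 or 10; 7.1 treats CK of 10 times ULN or more "as a grade 3 adverse event and grounds for holding the study drug". A CK between 1.5 and 3 times ULN with no other toxicity falls in neither 5.1 list.

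**What to change.** In 9.1, delete the two LDL-c conditions and state that patients who meet the Section 5.1 escalation criteria go to 40 mg. Put the same reference to 5.1 in the synopsis and 3.0, so that significant toxicity has one meaning. If the LDL-c rule is intended, add it to the synopsis, 3.0, 5.1 and 5.1.1, and redefine the high dose group in 9.2.1. Section 9.4 needs no change for this point.

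Separately, take CK out of the 1.5 times ULN line in 5.1, leaving the existing limit of 3 times ULN to govern escalation, and set one CK stopping level. Either confine the threefold rule in 9.5 to AST and ALT and use CK of 10 times ULN or more as in 7.1, or keep 9.5 and delete the 3–10 times line from 5.1. The investigators and the monitoring committee should choose, since it is a safety threshold.

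The cost is a short wording amendment, with no extra patients, visits or tests.

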9.2 Endpoints

9.2.1 Primary Endpoints:

Efficacy: The primary efficacy endpoint is mean percent change in fasting LDL-c (mg/dl) from week 2 (end of run-in period) to week 14

- The mean percent change in fasting LDL-c from week 2 to week 14 will be compared for the high dose group (rosuvastatin 20mg daily uptitrated to 40mg daily) and the moderate dose group (pravastatin 40mg daily).

Safety:

- All treatment-emergent adverse events, including but not limited to:
 - Incidence of adverse event-related study drug discontinuation (following initial 2 week wash-in) or hospitalizations
 - Grade 3 or greater adverse events;
 - Study drug-related symptoms
 - CK elevation > 3x upper limit of normal;
 - AST or ALT elevation >3x upper limit of normal;

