6.0 CLINICAL AND LABORATORY EVALUATIONS

6.1 Schedule of Events

	SCREEN- ING	WEEK 0 ^a	WEEK 2 ^a	WEEK 6 ^a	WEEK 10	Week 14/ or discontinuation
Informed Consent	X	X				
Medical and Medication History (including cardiovascular risk; HIV RNA and CD4, lipids)	X					
Complete Physical Exam	X					
Targeted Physical Exam		X	X	X	X	X
Height , Weight	X				X	
Vital Signs	X	X	X	X	X	X
Chemistry Panel, Liver Function Tests	X	X	X	X	X	X
Creatine Kinase	X	X	X	X	X	X
Fasting Lipid Panel	X	X	X	X	X	X
Pregnancy Test	X	X				X
Hematology, Hemoglobin A1c		X				X
Stored Plasma/Serum/PBMCs		X	X			X
Pharmacokinetics/dynamics			X	X		X
Randomization			X			
Dispensing of Study Drug		X	X	X	(X)*	
Adherence Assessment			X	X	X	X
Concomitant Medication Review	X	X	X	X	X	X
AE Determination		X	X	X	X	X
Phone Call					(X)*	
Statin Intolerance Survey			X	X	X	X

*(X) if on escalated rosuvastatin dose (40mg daily)

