7.1 Toxicity Management

7.1.1 General Reactions

Grade 1 or 2

Subjects who develop a Grade 1 or 2 toxicity may continue study treatment.

Grade 3

Subjects who develop a Grade 3 toxicity that is judged by the site investigator to be study drug-related should have the study drug held and the study team should be consulted. The subject should be followed closely and if the toxicity does not return to Grade ≤ 2 within 2 weeks, the study drug must be permanently discontinued with subject evaluations as per section 6.2.4.

If the study drug is resumed and the same Grade 3 toxicity recurs within 4 weeks of reintroduction, and the site investigator considers this AE related to the study drug, the drug must be permanently discontinued.

With a Grade 3 toxicity that is judged not related to the study drug by the site investigator, the study drug may be continued at the discretion of the site investigator in consultation with the study team.

Grade 4

Subjects who develop a Grade 4 toxicity will have the study drug permanently discontinued, with clinical assessments and laboratory testing as described for Grade 3 toxicity. If the investigator feels that the toxicity is clearly related to another cause and that the toxicity is not caused by the study drug, and after consultation with the study team, dosing may continue when the toxicity has resolved to Grade 2 or less.

Subjects experiencing Grade 4 toxicities should be followed closely with additional clinical assessments and laboratory testing as clinically indicated in consultation with the study team.

NOTE: Direct and indirect bilirubin elevations that reach Grade 4 elevations according to the DAIDS toxicity schema and are related to atazanavir are excluded from reporting.

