9.6.2 Secondary Analyses

Safety and tolerability data will be summarized by treatment group.

Adverse events (signs, symptoms, and diagnoses) will be analyzed and reported using the AIDS Clinical Trials Group (ACTG) medical dictionary and standardized coding for Signs, Symptoms, and Diagnoses for Clinical and Adverse Events. Adverse events will be tabulated by treatment group and will include the number of patients for whom the event occurred, the rate of occurrence, and the severity and relationship to study drug.

Incidence of clinical and/or laboratory toxicities. The safety and tolerability measures will include:

- Time to discontinuation of any study medication due to adverse events (AEs), --
- Proportion of Grade 3 or Grade 4 clinical AEs,
- Proportion of Grade 3 or Grade 4 laboratory abnormalities,
- Summaries of all treatment-related AEs

Possible future analyses

- Measures of the HIV reservoir size
- Soluble and cellular markers of immune activation and inflammation

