be documented on the Serious Adverse Events Form and faxed to the IND Sponsor, [name] at [name] within 24 hours of awareness. The IND Sponsor and the HILLCLIMBER Principle Investigator and Research Manager should be alerted about the faxed form by sending an email to [contact] and [contact] with the title: HILLCLIMBER SAE REPORT.

The FDA also requires sponsors to submit a written Safety Report of all serious and unexpected AEs. The study investigators in this study have the responsibility of promptly reporting all SAEs so that IND Sponsor can comply with these regulations. A non-blinded safety officer ([name]) will be available to review SAEs and determine the potential relation of the study drug to SAEs.

The protocol-defined expedited event reporting period for this protocol is the entire study duration for an individual subject (from study enrollment until study completion or discontinuation of the subject from study participation for any reason).

After the end of the protocol-defined reporting period stated above, sites must report serious, unexpected, suspected adverse drug reactions if the study site staff becomes aware of the event on a passive basis, i.e., from publicly available information.

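### The one symptom-specific safety item rests on unblinded attribution, while the scheduled Statin Intolerance Survey is named in no endpoint or analysis

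*Combined protocol and SAP*

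**What the plan says.** - Section 9.2.1 opens its safety endpoints with "All treatment-emergent adverse events, including but not limited to" and lists sub-items beneath. The only one specific to symptoms is "Study drug-related symptoms".
- Section 3.0 states: "This is a single center, randomized, controlled, open-label phase II trial". Section 9.1 repeats that the trial is open-label.
- Section 9.2.1 does not say who decides that a symptom is drug-related. Elsewhere, 7.1.1 refers to a Grade 3 toxicity "judged by the site investigator to be study drug-related", and 10.4 provides a non-blinded safety officer who "will be available to review SAEs and determine the potential relation of the study drug to SAEs". No blinded adjudication or causality criteria are described for the symptom item.
- The Schedule of Events in 6.1 marks the "Statin Intolerance Survey" at weeks 2, 6, 10 and 14, with no restriction to one arm.
- Section 6.3.4 requires signs and symptoms of Grade 1 or higher to be recorded after entry. Section 9.6.2 tabulates adverse events, symptoms included, by treatment group, giving patient counts and rates together with "the severity and relationship to study drug". It also plans summaries of the events considered treatment-related.

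**The concern.** A count of drug-related symptoms combines two things: how often symptoms occur, and how often someone who knows the treatment blames the drug. If the second differs between arms, the count differs even when symptoms do not.

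The design gives some reason to expect unequal scrutiny. Section 5.1 makes the week-6 rosuvastatin dose decision depend partly on whether toxicity is attributed to rosuvastatin; the pravastatin arm has no matching decision. The week-10 phone call in 6.1 applies only to patients on the escalated dose. Patients continuing pravastatin are on a drug they have already taken for two weeks without significant toxicity.

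The schedule already contains an instrument that could compare the arms without investigator attribution, with a baseline taken while everyone is on pravastatin 40 mg. The plan does not say how it will be used. Section 2.0 calls this a pilot for later studies powered for safety, so symptom rates by arm are an output that later planning may draw on.

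**Working it through.** **1. The plan's own computed figure.** The only one is the LDL-c sample size in 9.4 (difference 25 mg/dl, SD 20, two-sided alpha 0.05, power 0.80): n per arm = 2 × [20 × (1.960 + 0.842) / 25]² = 10.05, rounded up to 11. This reproduces the stated 11 per arm. It concerns LDL-c only; nothing is computed for symptoms.

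**2. Where the survey appears.** It has a row in 6.1. It is not mentioned in the objectives (1.1, 1.2), the evaluation instructions (6.3), the endpoints (9.2.1, 9.2.2) or the analyses (9.6.1, 9.6.2). Randomisation is at week 2 (4.3.2, 9.3), so the week-2 survey belongs to the common run-in and only weeks 6, 10 and 14 carry between-arm information. The plan does not say whether the week-2 survey precedes disclosure of the allocation.

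**3. What exists without attribution.** Three routes: the parent line of the safety endpoints in 9.2.1; the additional safety endpoint in 9.2.2; and the by-arm adverse event tables in 9.6.2, fed by the recording rule in 6.3.4. None uses a standardised questionnaire, and none specifies a comparison with the patient's own week-2 state.

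**4. How far attribution could move the count.** Recorded rate = true symptom rate × probability of attribution. The true rate is taken as equal in both arms, at the two ends of the 5–20% in 9.4. The attribution probabilities are assumptions; the documents give none.

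| True rate, both arms | Attribution, rosuvastatin / pravastatin | Recorded rates | Expected patients at 20 per arm |
|---|---|---|---|
| 20% | 50% / 50% | 10% vs 10% | 2.0 vs 2.0 |
| 20% | 60% / 40% | 12% vs 8% | 2.4 vs 1.6 |
| 20% | 80% / 40% | 16% vs 8% | 3.2 vs 1.6 |
| 5% | 60% / 40% | 3% vs 2% | 0.6 vs 0.4 |
| 5% | 80% / 40% | 4% vs 2% | 0.8 vs 0.4 |

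For example, 0.20 × 0.80 = 0.16 and 0.20 × 0.40 = 0.08. The spurious difference runs from 0 to 8 percentage points at a 20% true rate, and from 1 to 2 points at 5% when attribution is unequal as shown. The direction is also an assumption.

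**5. What a symptom comparison can show.** Take a true difference of 5% versus 20%, two-sided alpha 0.05, normal approximation with pooled variance under the null:

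power = Φ{[0.15 − 1.96 × √(2 × 0.125 × 0.875 / n)] / √[(0.05 × 0.95 + 0.20 × 0.80) / n]}

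At n = 20 this is Φ[(0.15 − 0.205) / 0.102] = Φ(−0.54), about 29%. At 15 and 25 per arm, matching the 30 and 50 participants in 9.4, it is about 23% and 36%. The 40 subjects in 3.0 are counted at run-in, so 20 per arm is the most that total can give.

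**The case against.** The strongest reply is that the attribution-free comparison is already planned. The drug-related item is a sub-item of an endpoint covering all treatment-emergent events, and 9.6.2 reports patient counts and rates by arm for all of them, with relationship as one descriptor among several. That stands. A reader might infer that the trial would have no symptom data free of attribution; the documents do not support that.

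A reader might also infer that the attributed count will show about twice as many symptoms on rosuvastatin. That is not supported either. The 80%/40% pair is an assumption, equal attribution gives no difference, and the documents contain no evidence on attribution in either arm.

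It is fair to add that no test, threshold or stopping rule uses the attributed symptom count; safety data are to be summarised. The survey may have been meant to feed the symptom item, although the plan does not say so. Its items, recall period and scoring are not in the available text. Appendix material is not available for review, so missing instrument detail should not be held against the plan. It does mean that simply replacing the listed item with the survey, at no cost, cannot be justified from these documents.

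Finally, survey answers also come from patients who know their drug. Using the survey removes the investigator's attribution but not open-label reporting bias.

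What the reply leaves unanswered is that the one item named for symptoms depends on attribution, and that a scheduled structured instrument has no stated use.

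**Conclusion.** The point holds as an inexpensive improvement to the safety reporting. The symptom-specific item in 9.2.1 depends on unblinded attribution, and the survey in 6.1 is named in no endpoint or analysis. The existing all-cause tables limit the damage but offer no standardised instrument and no pre-specified week-2 comparison.

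The bias cannot be sized from the documents; the table above is illustration only. At about 20 per arm even its most unequal row is a difference of 1.6 patients, so a few judgements could decide how the attributed count looks. Whichever measure is used, the comparison is descriptive. The LDL-c endpoint is not touched.

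The conclusion assumes that the survey is given to both arms, as the schedule row implies, and that its scoring allows a within-patient comparison, which needs confirming.

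**What to change.** - **9.2.1 and 9.6.2:** add the proportion of patients, by randomised arm and irrespective of attribution, with a new or worsened symptom on the survey at week 6, 10 or 14 compared with their own week-2 survey. Name the instrument, its scoring and what counts as worsened.
- **9.6.2:** make this and all-cause symptoms the main symptom comparison. Keep attributed symptoms as a supporting summary. State that the comparison is descriptive, and report how many patients in each arm lack a week-2 or later survey.
- **6.1:** require the week-2 survey to be completed before the allocation is disclosed to the patient and to the staff administering it.

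The cost is small but not nil: the instrument and its scoring must be written down, its suitability for a within-patient comparison checked, and the order of procedures at week 2 fixed. No new visit, sample or patient is needed, and no treatment rule changes.
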